## 12. Overview of study visit

Patients who agree to take part in the study will be asked to fast for 10 hours, where only water is allowed, before the study visit. Patients will also be asked to avoid exercise, caffeine (for example coffee, tea, and caffeine rich drinks), and chocolate in the 24 hours prior to the study visit; a clear instruction on which foods or drinks to avoid will be provided in the PIS.

On the study visit and after obtaining consent from study participants, their eligibility criteria to take part in the study will be assessed by the study investigator. Participants who fulfil the study inclusion/exclusion criteria will have full medical history obtained, and physical examination performed. If risk of OSA has not already been assessed in the clinic using the Berlin and the ESS questionnaires, these questionnaires will be completed. Participants with a high score on either the Berlin or ESS questionnaires will be provided with a portable sleep machine to take home; and a referral to the respiratory clinic will be arranged as per routine clinical practice. Information on how to use the sleep machine will be explained to the study participant by study doctor. Participants will be asked to return the machine the next day. Participants will have fasting bloods and early morning urine samples collected and stored. They will fill QoL and depression questionnaires. They will also be asked detailed questions about their fertility history. For women with regular periods, this visit will occur at the follicular phase of the cycle (day 1 – 7); while for oligomenorrhoeic women a random blood sample will be collected. The duration of the visit is approximately 1.5 hours.

A summary of patient activity during the study visit is provided in Table 2.

Visit	1
Participants	All
Duration	Approximately 1.5 hours
Informed consent	X
Medical history	X
Reproductive history	X
Anthropometry	X
Physical examination	X
Screening for OSA	X
Early morning urine sample	X
Blood tests	X
QoL and HAD questionnaires	X

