#### **11. Recruitment and choosing participants**

##### **– Method of recruitment**

Patients will be given the PIS by the study investigator or clinic nurse while sitting in the waiting area before being seen in the PCOS clinic. They will be advised to take the PIS home and call back if they are happy to take part in the study or if they have any question related to the study. In addition, an invitation letter and study PIS will be sent to patients who attended the PCOS clinic in the last 12 months. A list of patients who attended the PCOS clinic within the last year will be generated and from this list we will identify patients with confirmed diagnosis of PCOS and we will send the PIS and invitation letter to them by post.

Patients will also be recruited from the Weight Management Clinic and the reproductive endocrinology clinic where the PIS will be given to patients with a history of PCOS by the clinic doctor. Patients will be advised to take the PIS home and call back if they are happy to take part in the study or if they have any questions related to the study.

A poster inviting women with a history of PCOS to take part in the study will be displayed at University Hospital Coventry and an e-poster will be displayed at the hospital intranet. Women who answer the advert will be sent the PIS and advised to call back if they would like to take part or if they have any question about the study.

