##### **– Procedures to assess study suitability**

Initial biochemical and clinical screening to confirm the diagnosis of PCOS and investigate the likelihood of OSA will be performed as part of routine clinical care in the National Health Service (NHS).

For patients who self-refer through the advertisement, the study doctor will clarify the diagnosis of PCOS with them on the phone and if the diagnosis is not clear, they will be offered the chance to be seen in the PCOS clinic if they wish.

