## - Participants

38 women will be recruited after fulfilling the inclusion and exclusion criteria. Study participants will be screened for OSA using Berlin and Epworth Sleepiness Scale (ESS) questionnaires and if both were normal then no further testing for OSA is required. If the score on either of the questionnaires was abnormal then home-based sleep studies will be arranged and the patient will be referred to the Respiratory Physician as per routine clinical care.

OSA will be assessed by a single overnight home-based cardiorespiratory sleep study using a portable multichannel device (Alice PDx, Philips, US) and scored in accordance with the International Classification of Sleep Disorders (ICSD-3) (American Academy of Sleep Medicine 2014). The scoring of the sleep studies will be performed by [name], Respiratory Physician, or a sleep technician. Sleep studies with <4 hours of adequate recordings will be repeated and excluded if the quality remained poor. OSA is defined by either an AHI of  $\geq 5$  with daytime sleepiness as well as gasping, choking or snoring; or an AHI of  $\geq 15$  in the absence of symptoms (American Academy of Sleep Medicine 2014).

Participants will be divided into two groups depending on the results of the ESS and Berlin questionnaires and sleep studies:

1. PCOS low risk OSA: women with PCOS with either normal scores on both the ESS and Berlin questionnaires, or who had normal sleep studies.
2. PCOS OSA: women with PCOS who had sleep studies confirming the presence of OSA.

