## **15. Ethical Considerations**

The study will be performed subject to favourable opinion from NHS Research Ethics Committee (REC), and the NHS Health Related Authority (HRA), and approvals from University Hospitals Coventry and Warwickshire NHS Trust Research and Development Department. Patients will be offered the PIS by a nurse while they are sitting in the waiting area before being seen in the PCOS clinic. The PIS and a study invitation letter will also be sent to patients who attended the PCOS clinic in the last 12 months.

We excluded women who do not speak adequate English from the study. However, almost all the women attending the PCOS clinic at University Hospital Coventry speak and understand English adequately.

We are asking study participants to fast before obtaining their written consent. However, these women will already have a confirmed diagnosis of PCOS as they will be recruited from the PCOS clinic. They will also have had enough time to read the PIS to consider whether they would like to take part in the study. When a patient calls back to express interest in the study and book a study visit, the study doctor will run through the inclusion/exclusion criteria with the patient and obtain her verbal consent on the phone to ensure she is happy to fast before attending the study visit and signing the written consent form. This will save the study participant time and effort, particularly as we are not paying for participants' transport or car parking fees.

Depending on the scores from the HAD scale, this study may result in the identification of women with PCOS who may suffer from depression or anxiety. Women with high scores on the HAD questionnaire will be advised to attend their GP for further evaluation of their mood.

Study participants who are sleepy during the daytime will be advised not to drive if feeling sleepy. Those with a confirmed diagnosis of OSA will be seen in the respiratory clinic and issues related to driving and DVLA regulations will be discussed with them by the Respiratory physician as per routine clinical care; this information will also be included in the PIS.

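### An old normal Berlin/ESS result from the clinic can place a woman in the low-risk group untested, although her quality of life is measured at the visit

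*Combined protocol and SAP*

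**What the plan says.** Section 12 (Overview of study visit) gives the rule for the prose description of the visit: "If risk of OSA has not already been assessed in the clinic using the Berlin and the ESS questionnaires, these questionnaires will be completed". Table 2 in the same section lists "Screening for OSA" as an activity of visit 1, with all women as participants and no condition attached.

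Section 11 (Procedures to assess study suitability) places the assessment of OSA likelihood in routine NHS care. Under Method of recruitment, one of several routes is by post: "an invitation letter and study PIS will be sent to patients who attended the PCOS clinic in the last 12 months". Section 10.1 says the same.

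Section 11 (Participants) then fixes what follows from the scores. For the two questionnaires, "if both were normal then no further testing for OSA is required". The low-risk group consists of "women with PCOS with either normal scores on both the ESS and Berlin questionnaires, or who had normal sleep studies". On the other branch, "If the score on either of the questionnaires was abnormal then home-based sleep studies will be arranged". None of these rules mentions the date of the questionnaire.

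Quality of life, HAD and anthropometry are all collected at the study visit (section 12 and Table 2). Section 9 calls the study cross-sectional, and section 14.2 makes OSA group the predictor of interest.

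**The concern.** In a cross-sectional comparison, exposure and outcome should describe the same time. Here the outcome is dated to the visit, but for some women the exposure may be dated to an earlier clinic attendance.

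The two kinds of outdated screen are treated differently. An outdated abnormal score still leads to a sleep study, which settles the group. An outdated normal score leads to nothing further, so the woman stays in the comparator whatever her present state. Misplacement from this source therefore runs only from OSA into the low-risk group. If OSA lowers quality of life, as the hypothesis states, this shrinks the observed difference.

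The items can change over months. The ESS in the appendix asks about recent times. Category 3 of the Berlin questionnaire depends partly on BMI above 30. BMI is measured afresh at the visit, but the protocol does not feed that measurement back into a Berlin result obtained earlier.

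Separately, the prose and Table 2 of section 12 can be followed in two different ways, and staff need to know which applies.

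**Working it through.** **1. Reproducing the plan's sample size.** Section 14.1 and Table 3 give a mean difference of 17.8, a pooled SD of 18.2, 15 women with OSA and 23 at low risk, two-sided 5% significance and 80% power.

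- Pooled SD: √((18.72² + 17.67²)/2) = 18.20. Effect size: 17.8/18.2 = 0.98.
- Two-sample t-test, 15 + 23 − 2 = 36 degrees of freedom, noncentrality 0.978 × √(15 × 23/38) = 0.978 × 3.013 = 2.95.
- Power from the noncentral t distribution: about 82%. The stated total of 38 is reproduced.

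**2. How many women could be affected.** The documents do not say how many women were screened in clinic, how long before the visit, or how often a normal score becomes abnormal. The shares below are assumptions.

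- Base: only normal screens can cause the error. Table 3 plans 23 low-risk women. Some of them would have entered through a normal sleep study instead, so under the planned split 23 is an upper limit for the base.
- Assumed: 20% to 50% of these screens are carried forward from clinic, and 5% to 15% of those would now be abnormal.
- Low end: 0.20 × 23 × 0.05 = 0.23. High end: 0.50 × 23 × 0.15 = 1.73.
- These 0.2 to 1.7 women would newly screen positive. Only those with OSA on a sleep study are misplaced, because the rest belong in the low-risk group anyway. If half had OSA (a further assumption), 0.1 to 0.9 would be misplaced.

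**3. Effect of one misplaced woman.** Assume that she has the mean of the OSA group.

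- Expected difference: 17.8 × (1 − 1/23) = 17.0.
- Effect size: 17.03/18.2 = 0.94. Noncentrality: 0.936 × 3.013 = 2.82.
- Power: about 78%. If the mixture also widens the low-risk SD, power is about 77%.

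These power figures are for the unadjusted comparison on which section 14.1 is based. They are not for the adjusted models of section 14.2.

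**The case against.** The strongest reply is that the problem may hardly arise. Women approached at a current clinic attendance will usually have a recent screen. A letter recruit who was never screened in clinic completes both questionnaires at the visit under the existing rule. Section 11 describes the routine screening prospectively, which is compatible with screening close to enrolment. And if Table 2 governs, everyone is screened at the visit and the gap closes. All of this stands as a limit on the size. It does not remove the rule: the specific sentence is conditional, the table is introduced as a summary, and nothing caps the age of a clinic score.

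Three stronger readings are tempting, and the documents do not support them.

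- A reader might infer that screens are known to be up to 12 months old. Twelve months is the look-back on clinic attendance for the letter route. No section says that the questionnaires were completed at those attendances, and the look-back is not an upper limit either, since the visit follows the letter.
- A reader might infer that skipping the ESS removes the only prompt for driving advice. Section 15 ties that advice to being sleepy, not to a score: "Study participants who are sleepy during the daytime will be advised not to drive if feeling sleepy". It also puts driving information in the information sheet, and a full medical history is taken at the visit. What is missing is a specified repeat measure of sleepiness that feeds the grouping.
- A reader might apply the assumed shares to all 38 women (0.20 × 38 × 0.05 = 0.4 to 0.50 × 38 × 0.15 = 2.9) and count each as misplaced. That includes women whose abnormal screen already leads to a sleep study, and it treats a positive questionnaire as OSA. A dilution of 2/23, or 9%, lies above the range in the working.

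**Conclusion.** The point holds as a cheap improvement. The text allows an undated normal clinic screen to decide group membership with no later check, and its prose and Table 2 need to be reconciled. The direction is clear: contamination of the comparator only, and attenuation if OSA lowers quality of life.

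The size is uncertain and probably small. On the assumed shares, 0.2 to 1.7 women would newly screen positive and fewer would have OSA. One such woman costs about 0.8 points of the expected difference (17.8 − 17.0) and about 4 points of power (82% to 78%). That would bring power slightly below the stated 80%, but the documents give no frequency from which to say that it will happen. Confidence is high about the wording and low about the number of women affected.

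**What to change.** In section 12, replace the conditional sentence with a rule that all participants complete the Berlin and ESS questionnaires at the study visit, in agreement with Table 2. State that the visit scores update any earlier normal screen for the purposes of sleep testing and study group. State also that an earlier abnormal clinic score still leads to the sleep study that section 11 already requires, so that a normal score at the visit cannot cancel it. Record the date and scores of any earlier clinic screen, so that the interval to the visit and the number of changed results can be reported.

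The cost is a few minutes per woman for two short forms already in the appendix, and possibly a few more home sleep studies with the existing device. The sample size of 38 does not change.

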### 10.2 Inclusion criteria

- Women with PCOS, defined by the Rotterdam criteria as 2 out of 3:
  1. Oligo/anovulation
  2. Clinical or biochemical evidence of hirsutism
  3. Polycystic ovaries on ultrasound.

And the exclusion of other disorders with similar presentation including NC-CAH, androgen secreting tumours, Cushing's syndrome; thyroid disorders and prolactinomas.

- Age  $\geq$  18 years.
- Able to provide written consent.
- Able to adequately understand English.
- Patients with unknown diagnosis of OSA, or who were investigated in the past and either found not to have OSA, or found to have OSA and are not on CPAP therapy.

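### The visit plan lists OSA screening before self-rated QoL and does not protect the order, so women may rate QoL knowing they were flagged, which may bias the primary comparison towards the hypothesis.

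*Combined protocol and SAP*

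**What the plan says.** Screening may take place before or at the study visit. Section 12 says: "If risk of OSA has not already been assessed in the clinic using the Berlin and the ESS questionnaires, these questionnaires will be completed". It continues: "Participants with a high score on either the Berlin or ESS questionnaires will be provided with a portable sleep machine to take home", with a referral to the respiratory clinic. It then covers device instruction, the return of the device, and blood and urine samples. Only after these does it say "They will fill QoL and depression questionnaires". Table 2 lists screening for OSA above the QoL and HAD questionnaires.

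Section 11 (Participants) defines the two groups. The low-risk group is "women with PCOS with either normal scores on both the ESS and Berlin questionnaires, or who had normal sleep studies". The PCOS OSA group is "women with PCOS who had sleep studies confirming the presence of OSA". The study arranges a sleep study only when the Berlin or ESS result is abnormal.

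Section 14.2 names the PCOSQ and WHOQOL-BREF domain scores as the primary outcomes. Both are completed by the woman herself, as is the HAD scale, a secondary measure. The only masking in the protocol is in section 13.2, for the operator of the urinary isoprostane assay. Section 7 sets the direction of the hypothesis: worse QoL in women with PCOS and OSA.

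**The concern.** A woman who is handed a sleep recorder and referred to a chest clinic knows that she screened positive. If she then rates her QoL and mood, that knowledge may lower her answers whatever her breathing during sleep. The knowledge is not evenly spread. Women who reach the PCOS OSA group through the study's own screening were all flagged; women who were never flagged are all in the low-risk group. Any lowering of ratings through awareness would therefore look like an effect of OSA, in the direction the study expects.

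Awareness is not among the confounders named in section 14.2, and it is tied too closely to group for adjustment to separate it reliably. The protection has to come from the design of the visit, and at present the plan has none.

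**Working it through.** **1. The order in the text and the table.** Both place OSA screening before the QoL and HAD forms. The text also places device hand-out and referral before them. No section requires the reverse, and none keeps the screening result from the woman before she completes the forms.

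**2. The plan's own figure.** Inputs from section 14.1 and Table 3: means 75.41 and 57.65, SDs 18.72 and 17.67, groups of 15 and 23, two-sided 5%.
- Pooled SD = √((18.72² + 17.67²)/2) = 18.2.
- Difference = 75.41 − 57.65 = 17.76, stated as 17.8. Effect size = 17.8/18.2 = 0.98.
- Power from the non-central t with 36 degrees of freedom is 0.82; with the Mann-Whitney efficiency factor 3/π it is 0.80.

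The stated total of 38 is reproduced and is not in dispute. The point concerns bias, not sample size.

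**3. Size of a possible bias.** The documents do not say whether awareness changes ratings, by how much, or how many low-risk women will have been flagged. The following are assumptions:
- s: fall in the rated physical domain among flagged women, 3 to 10 points.
- f: share of the low-risk group who were flagged and then had a normal sleep study, 20 to 60%.
- All of the PCOS OSA group were flagged, and the true effect of OSA is zero.

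The mean of the PCOS OSA group falls by s and that of the low-risk group by s × f. So:

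Spurious difference = s − s × f = s × (1 − f)

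The false-positive rate is the two-sided rejection probability of the unadjusted t-test. Its non-centrality is (spurious difference/18.2) × √(15 × 23/38), where the square root is 3.01.

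| s (points) | f | Spurious difference | Share of 17.8 | False-positive rate |
|---|---|---|---|---|
| 0 | any | 0 | 0% | 5.0% |
| 3 | 60% | 3 × 0.4 = 1.2 | 7% | 5.4% |
| 5 | 40% | 5 × 0.6 = 3.0 | 17% | 7.7% |
| 8 | 40% | 8 × 0.6 = 4.8 | 27% | 12.1% |
| 10 | 20% | 10 × 0.8 = 8.0 | 45% | 25% |

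The last row needs both unfavourable assumptions at once. The planned analysis is an adjusted linear model, so these rates are a guide and not a forecast of its behaviour.

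**The case against.** Several points on the other side are sound.

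- **The listed order is not a stated order of conduct.** Section 12 is an overview. It says "Participants will be asked to return the machine the next day" before it mentions the samples and forms of the same visit. It puts fertility questions last, where Table 2 puts reproductive history third. A reader might infer that every woman in the PCOS OSA group is told of a positive screen before she rates her QoL; the documents do not establish that. What stands is that the order is unprotected, and that the only sequence a site can read in the text and the table is the unfavourable one.
- **Knowing one was flagged is not knowing one's group.** If QoL is completed at the visit, the study's sleep test has not yet been done. Flagged women with normal sleep studies share the awareness and sit in the comparison group. This dilutes the bias by the factor (1 − f) but does not remove it unless the whole low-risk group was flagged.
- **Sleepiness is not affected in this way.** A reader might extend the argument to it, but it is measured by the ESS, which is itself a screening tool and is completed before it can produce a flag.
- **The driving advice in section 15 adds nothing.** It has no stated timing and applies to sleepy women in either group.
- **Re-ordering the visit reaches only some women.** Section 11 makes assessment of OSA likelihood part of routine care, so some will have been screened in clinic. Section 10.2 also admits women "who were investigated in the past and either found not to have OSA, or found to have OSA and are not on CPAP therapy". The documents do not say how many women this covers.

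**Conclusion.** The concern holds as a possible bias of unknown size. The primary outcome is self-rated, screening is listed ahead of it, nothing masks the result, and being flagged is linked to group by design. If awareness lowers ratings, the direction follows from the group definitions: towards the hypothesis.

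A reader might infer that the primary comparison is biased as planned. The documents do not support that, because they give no evidence that an awareness effect exists and do not fix the order of conduct. The range of 1.2 to 8.0 points, with a false-positive rate of 5.4 to 25%, rests wholly on the assumed shift and flagged share, uses an unadjusted t-test with 15 and 23 women and an SD of 18.2, and is illustrative only. If awareness has no effect, the rate stays at 5%.

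The change is worth making because it is almost free and protects the primary comparison for every woman screened at the visit.

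**What to change.** 1. In section 12 and Table 2, state that PCOSQ, WHOQOL-BREF and HAD are completed after consent and the eligibility check, before Berlin and ESS are completed or scored, and before any device hand-out or referral.
2. For women already screened in clinic or previously investigated for OSA, record on the case report form whether they knew the result, and tabulate this by group.
3. In section 14.2, add a supportive comparison of OSA-confirmed with OSA-negative women among those flagged, who share the awareness of a positive screen. Under the assumed 20 to 60%, the OSA-negative side would have about 5 to 14 women (0.2 × 23 = 4.6; 0.6 × 23 = 13.8), so it can support the main result but not replace it.

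Cost: one re-ordered visit and one extra case report form field, with no added visit time and no change to the planned 38. The protection is partial, because women screened or investigated before the visit cannot be made unaware.
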